Name Modified Date

CS14.0 Are you using UPMC facilities and/or UPMC patients during the conduct of your research study?

* Yes

If Yes, upload completed Research Fiscal Review Form:

Name Modified Date
<FRIAR IOPI.docx> 9/2/2015 11:44 AM

View: CS15.0 - CS15.0.1(a)

Cover Sheet Section

CS15.0 Indicate the sites where research activities will be performed and/or private information will be obtained.

Choose all sites that apply and/or use **Other** to include sites not listed:

Sites:
UPMC

University of Pittsburgh

Campus:

There are no items to display

List university owned off-campus research sites if applicable:

UPMC

Sites:

UPMC Presbyterian

UPMC Montefiore

UPMC Shadyside

UPMC Cancer Network Sites:

Site

There are no items to display

If you selected **School, International or Other**, list the sites:

***For research being conducted at non Pitt or UPMC sites, upload a site permission letter granting the researcher permission to conduct their research at each external site:**

Name Modified Date

CS15.1 **Have you, [name] , verified that all members of the research team have the appropriate expertise, credentials, and if applicable, hospital privileges to perform those research procedures that are their responsibility as outlined in the IRB protocol?**

* Yes

CS15.2 **Describe the availability of resources and the adequacy of the facilities to conduct this study:**

* The UPMC Dept. of Otolaryngology treats individuals with qualifying diagnoses for this research at both UPMC Shadyside and UPMC Presbyterian/Montefiore. Each clinical office has board certified

clinicians in their respective fields that are extremely qualified in treating patients with swallowing difficulties. Additionally, clinicians have extensive research experience. Each clinic has both physicians and speech language pathologists who will be able to identify, educate, enroll and implement the minimal amount of research procedures necessary for the conduct of this research during clinical appointments of potential subjects. The study team has access to protected servers for data security and information protection whenever data is generated, collected, or stored.

View: CS16.0

Cover Sheet Section

CS16.0 **Special Research Subject Populations:**

Categories
None

View: CS17.0

Cover Sheet Section

CS17.0 **Does your research involve the experimental use of any type of human stem cell?**

* No

View: Clinical Trial Study

NIH Definition of a Clinical Trial

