2.4.1 Provide a justification for discontinuing subjects from known effective therapy for the

purpose of study participation.

2.4.2 **Describe the risks to subjects associated with discontinuing them from known effective therapy for the purpose of study participation.**

View: 2.05

Section 2 - Research Design and Methods

2.5 **Will screening procedures (i.e., procedures to determine research subject eligibility) be performed specifically for the purpose of this research study?**

* No

2.5.1 **List the screening procedures that will be performed for the purpose of this research study. Do NOT include the inclusion/exclusion criteria in this section as they will be addressed in section 3; questions 3.13 and 3.14.**

2.5.2 **What steps will be taken in the event that a clinically significant, unexpected disease or condition is identified during the conduct of the screening procedures?**

Addressed below:

Participants will be under the clinical care of a member of the Department of Otolaryngology. Any disease or condition identified during the course of this research will be addressed following standard clinical procedure.

View: 2.06

Section 2 - Research Design and Methods

2.6 **Provide a detailed description of all research activities (e.g., all drugs or devices; psychosocial interventions or measures) that will be performed for the purpose of this research study.**

This description of activities should be complete and of sufficient detail to permit an assessment of associated risks.

At a minimum the description should include:

- **all research activities**
- **personnel (by role) performing the procedures**
- **location of procedures**
- **duration of procedures**
- **timeline of study procedures**

Individuals seen by Department of Otolaryngology physicians/clinicians, having developed treatment associated dysphagia after completing non-operative treatment with chemoradiation or radiation therapy alone, for oral, oropharyngeal, hypopharyngeal or laryngeal cancer, will be approached for participation during the course of usual clinical care in the Dept. of ENT clinical offices designated in this protocol.

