Once enrolled through written informed consent, research participants will be assigned to either "standard therapy" or to "standard therapy with IOPI" treatment group by a clinical investigator. This assignment will be in an alternating fashion based on date of enrollment. IOPI treatment consists of 10 repetitions of the IOPI exercises, three times a day on three days per week for 8 weeks. It will take 30 minutes to train the subject on how to do the exercises and record them and that it takes 5-10 minutes to complete 30 repetitions of the exercise. Subjects will be completing a diary related to their exercise regimen.

Subjects will undergo a standard of care modified barium swallow study by clinical staff prior to the onset of therapy to obtain baseline measurements of airway protection and oropharyngeal kinematic function. They will also be asked to complete a Visual Analog Scale (VAS) to rate their dysphagia prior to initiation of therapy, therapy by marking an "X" on a 100mm line indicating their perception of the severity of their dysphagia (0 = least severe, 100 = most severe). They will also be asked to complete a dietary assessment tool/questionnaire consisting of 10 items (EAT-10). Tongue isometric pressure generation (strength) will be measured with the IOPI. This requires the subject to press a small plastic air-filled bulb between the tongue and hard palate, which transfers isometric pressure on the IOPI. The Functional Oral Intake Scale (FOIS) will be used by the clinician to rate current level of oral intake. Finally subjects will be weighed.

Approximately 8 weeks after the initiation of therapy ("standard" or "standard w/ IOPI") individuals will be asked to complete the VAS and the EAT-10, and the clinician will repeat the FOIS and weigh the subjects, once again at their 8-week standard of care clinical follow up visit. 8 weeks is the usual standard of care follow up visit. A modified barium swallow (MBS) test will also be performed as part of standard of care at about the 8 week time point (after therapy). Finally isometric pressure (tongue strength) will be measured at this point.

At 8 weeks, individuals who were assigned to the "standard therapy only" group, who still require swallowing therapy, will be asked if they would like to add the IOPI to their therapy

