We will perform t-tests to compare the dependent variable values from each measure (penetration-aspiration scores, pharyngeal retention scores, swallow kinematic measures, tongue pressure scores, EAT-10 scores, VAS scores, and patient weight. We may also perform ANOVAs and post hoc analyses to determine the main effect of treatment condition on the dependent variables, and to determine the presence of any interaction effects, and single subject analyses using the C statistic, to determine individual effect sizes for individual participants. Analyses will be designed to compare performance at the following time points:

1. between groups comparisons at time 1 (start of treatment) and at 2 (end of treatment) to evaluate differences between groups at the start and end of 8 weeks of therapy.
2. within groups comparisons between time 1 and 2 (standard therapy vs. standard therapy + IOPI) to evaluate the magnitude of differences from beginning to end of therapy.
3. within group comparison (standard treatment crossover only) at time 1 and time 3 (8 weeks after crossover of standard treatment subjects into standard therapy + IOPI) to evaluate the magnitude of differences from beginning of therapy to end of second phase of therapy (combined standard therapy, with crossover to standard + IOPI).

View: 2.19 - 2.19.6

Section 2 - Research Design and Methods

2.19 Will this research be conducted in (a) a foreign country and/or (b) at a site (e.g., Navajo Nation) where the cultural background of the subject population differs substantially from that of Pittsburgh and its surrounding communities?

* No

Note that copies of training records, licenses, certificates should be maintained in the study regulatory binder and are subject to audit by the Research Conduct and Compliance Office (RCCO).

In addition, individuals planning to conduct human subject research outside the United States must complete an optional module on the CITI training website: International Studies. [Click here](#) to access the instruction sheet for accessing optional CITI modules.

2.19.1 Address the following for each of the foreign/culturally different sites where this research will be conducted:

- Name of site
- Name of authorized individual (e.g., IRB Chair) from the local IRB or other human subject protections entity that is responsible for the review and approval of the project; upload approval letter with an English translation, if applicable

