Upload recruitment letters/scripts/text:

Name Modified Date

Research Registry

List the IRB approval number and title for each registry source:

4.2 Provide a detailed description of your recruitment methods, including identifying and initiating contact with participants:

Potential research subjects will be initially contacted at the University of Pittsburgh Medical Center Department of Otolaryngology outpatient clinic while there for routine clinical evaluation. They will be approached by their clinician who may also be an investigator of this research project. The investigator or clinician, who will be trained in all research procedures, will present information about this research study. If the potential research subject is interested, the informed consent process will be initiated.

Note: Questions jump from 4.2 to 4.6 as questions 4.3-4.5 have been removed and the information is now captured in 4.1

View: 4.06

Section 4 - Subject Recruitment and Informed Consent Procedures

4.6 Are you requesting a waiver to document informed consent for any or all participants, for any or all procedures? (e.g., a verbal or computerized consent script will be used, but the subjects will not be required to sign a written informed consent document.

This is not a waiver to obtain consent.

* No

4.6.1 Identify the specific research procedures and/or the specific subject populations for which you are requesting a waiver of the requirement to obtain a signed consent form.

If not all, identify the specific procedures and/or subject populations for which you are requesting a waiver:

4.6.2 Indicate which of the following regulatory criteria is applicable to your request for a waiver of the requirement to obtain a signed consent form.

45 CFR 46.117(c)(1) That the only record linking the subject and the research would be the consent document and the principal risk would be potential harm resulting from a breach of confidentiality. Each subject will be asked whether the subject wants documentation linking the subject with the research, and the subject's wishes will govern; or

45 CFR 46.117(c)(2) That the research presents no more than minimal risk of harm to subjects and involves no procedures for which written consent is normally required outside of the research context.

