- process for child assent and parental permission
 - continued participation if a child subject turns 18 during participation
- process for obtaining proxy consent and assent for decisionally impaired subjects
 - continued participation if subject regains capacity to consent

The potential research subject will be approached by their clinician who may also be an investigator on this research study. The clinician or investigator will provide information about participation, including the purpose of the study, the potential risks and benefits of study participation, and their rights as a research subject. The clinician or the investigator will go through the informed consent document with the potential research subject prior to enrollment. The investigator and/or clinician will answer any questions that the potential research subject may have about this research study. Consent will ultimately be obtained by the clinician or one of the investigators on this project as approved by the IRB.

4.13 Are you requesting an exception to either IRB policy related to the informed consent process?

- For studies involving a drug, device or surgical procedures, a *listed physician* investigator is required to obtain the written informed consent unless an exception to this policy has been approved by the IRB
- For all other studies, a *listed* investigator is required to obtain consent (Note: In order to request an exception to this policy, the study must be minimal risk)

* Yes

If Yes, provide a justification and describe the qualifications of the individual who will obtain consent:

We are requesting an exception to the IRB policy requiring a "listed physician investigator" to obtain written informed consent from participants.

The reason for this request is that additional clinicians in the Department of Otolaryngology will have the required knowledge to complete the informed consent process. Currently, there are 5 Speech Language Pathologists (currently not listed as co-investigators) that will be directly involved in the care of the participants. These individuals will be assisting with the swallowing testing as well as instructing the subjects in the proper therapy techniques and proper use of the IOPI device. With proper instruction on the details of the protocol, these additional 5 SLPs who are assisting directly with the care of these individuals will be adequately qualified to answer questions related to this research.

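### Two clinical offices enrol and treat patients, but neither the assignment rule nor the analysis mentions clinic; adding it is a cheap, minor improvement

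*Combined protocol and SAP*

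**What the plan says.** CS15.2 states that the department "treats individuals with qualifying diagnoses for this research at both UPMC Shadyside and UPMC Presbyterian/Montefiore". It adds: "Each clinic has both physicians and speech language pathologists who will be able to identify, educate, enroll and implement" the study procedures. CS15.0 ticks three UPMC sites, which CS15.2 groups as two offices. Section 2.6 also uses the plural, placing recruitment "in the Dept. of ENT clinical offices designated in this protocol". Section 4.2 uses the singular, describing contact at the "University of Pittsburgh Medical Center Department of Otolaryngology outpatient clinic while there for routine clinical evaluation". This is loose wording that should be aligned with CS15.2, but it does not withdraw the second office.

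On assignment, 2.6 says a clinical investigator allocates patients, and: "This assignment will be in an alternating fashion based on date of enrollment". It does not mention clinic or stratification, and does not say whether the sequence is common to both offices.

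On analysis, 2.18 says: "We will perform t-tests to compare the dependent variable values from each measure". It continues: "We may also perform ANOVAs and post hoc analyses to determine the main effect of treatment condition on the dependent variables". Interaction effects are mentioned but not tied to clinic. Clinic is also not among the record items listed in 2.14.

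On delivery, 4.13 describes five further speech language pathologists: "These individuals will be assisting with the swallowing testing as well as instructing the subjects in the proper therapy techniques". Their distribution between the offices is not given. No section describes how standard therapy or measurement is made uniform across offices.

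**The concern.** Standard therapy, the barium swallow and the FOIS rating are usual care delivered in the offices. If the offices differ in therapy, testing practice or case mix, and if the arms draw unequally on the two offices, part of that difference is carried into the IOPI comparison. Even with balanced arms, variation between offices stays in the error term of a plain t-test and costs some precision.

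This is separate from the predictability of alternation. One unstratified random list would leave the same chance imbalance and the same missing term in the analysis. The study is called a pilot, but 1.1 gives its purpose as determining effectiveness and 2.18 tests it by comparing groups, so protecting that comparison at low cost is worthwhile.

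**Working it through.** **Inputs from the documents.** 50 patients per arm, 50 + 50 = 100 in total (3.10, 3.11); two offices (CS15.2); alternating assignment (2.6). Section 3.12 bases enrolment on feasibility and gives no alpha, power, effect size or SD, so there is no sample-size calculation to reproduce.

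**Assumptions.** Patients split evenly between offices; an outcome difference between offices of D = 0.5 within-office SD; two-sided alpha 0.05. None of these is in the documents.

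**Step 1: chance imbalance with one shared list.** Let g be the difference between arms in the share of patients from one office. With 50 per arm and each enrolment equally likely at either office:

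- SD(g) = √(0.25/50 + 0.25/50) = √0.01 = 0.10
- 95% range: 1.96 × 0.10 ≈ 0.20
- median of |g|: 0.6745 × 0.10 ≈ 0.067; the simulated value is 0.06, because g moves in steps

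Simulation gives a mean of zero and a 95th percentile of 0.20. If the larger office has 70% or 80% of patients, the 95th percentile is 0.18 or 0.16.

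**Step 2: error in the IOPI comparison.** Error = g × D.

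- Typical: 0.06 × 0.5 = 0.03 SD
- Upper end: 0.20 × 0.5 = 0.10 SD
- At D = 0.3 the upper end is 0.06 SD; at D = 0.8 it is 0.16 SD

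**Step 3: effect on the test.** For scale, the difference detectable with 80% power at 50 per arm is (1.96 + 0.8416) × √(2/50) = 0.56 SD. Omitting clinic raises the SD to √(1 + 0.25 × 0.5²) = 1.031, so 0.56 becomes 0.56/1.031 = 0.543 and power is about 0.775 by the normal formula. In simulation with one shared list, the plain t-test has power 0.774, against 0.793 with clinic in the model. Type I error of the plain t-test is 0.049 at D = 0.5 and 0.051 at D = 1.0.

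**Step 4: sensitivity to the arrival pattern.** Let q be the probability that the next enrolment is at the other office. The documents say nothing about q, so both directions are shown, with one shared alternating list and D = 0.5.

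| q | 95th percentile of g | error, SD | type I error, plain t-test |
|---|---|---|---|
| 0.1 | 0.06 | 0.03 | about 0.05 |
| 0.3 | 0.12 | 0.06 | about 0.04 |
| 0.5 | 0.20 | 0.10 | about 0.05 |
| 0.7 | 0.30 | 0.15 | about 0.06 |
| 0.9 (stress case) | 0.56 to 0.58 | 0.28 to 0.29 | about 0.10 |
| 1.0 (stress case) | 1.00 | 0.50 | 0.70 |

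With clinic in the model, type I error is near 0.05 for q from 0.1 to 0.9. At q = 1, clinic and arm coincide and no adjustment can separate them.

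**Step 5: if each office keeps its own alternating list.** The 95th percentile of g is 0.004 to 0.014 (larger office 50% to 80% of patients), so the error at D = 0.5 is under 0.01 SD. What remains is lost precision: with an even split, the plain t-test is slightly conservative (type I error 0.041) and its power is 0.773, against 0.791 with clinic in the model.

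**The case against.** The strongest reply is that this is ordinary covariate imbalance of modest size. Under neutral arrival the imbalance has mean zero, the type I error is intact and the power loss is about two percentage points. The same could be said of tumour site, stage or radiation dose. The offices belong to one department, CS11.0 answers no to the multi-centre question, and the study is sized on feasibility. Many outcomes leave little room for an office's rating habits: EAT-10 and VAS are completed by the patient, weight and tongue pressure are instrument readings, and kinematic measures use image-processing software. FOIS is clinician-rated but is not among the measures that 2.18 lists for t-tests. All of this stands, and it sets the low severity.

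Three stronger readings are tempting, and the documents support none of them.

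- A reader might infer that one sequence is definitely shared and so leaves the offices unbalanced. Section 2.6 does not say so. With a list per office, the arms would already be nearly balanced.
- A reader might infer systematic bias of 0.29 or 0.5 SD. Those figures need both an assumed 0.5 SD office difference and enrolments that almost always alternate between offices. Nothing indicates either. Clustering by office is equally compatible with the text and would make balance better than chance.
- A reader might treat two patients enrolled on one date at different offices as a clinic problem. Ties arise within one office as well, so they are a feature of date-based alternation.

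What the objection does not remove is that two sets of premises and staff deliver care and testing, and that the plan neither balances nor adjusts for this.

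**Conclusion.** The point holds as a minor one. Two offices enrol patients and carry out procedures, while clinic is absent from the assignment rule and from the analysis, and the list structure is unstated. With one shared list, an even split, no arrival pattern and a 0.5 SD office difference, the error in the IOPI comparison is about 0.03 SD typically and 0.10 SD at the upper end, against a detectable difference of 0.56 SD. Type I error stays near 0.05. The larger figures in the table are stress cases only.

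The conclusion rests on assumed values for the office difference, the split and the arrival pattern. The documents do not show that the offices differ. The clinic term is useful under either list structure, because it recovers the lost precision in both.

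**What to change.** In 2.18, include clinical office (Shadyside versus Presbyterian/Montefiore) as a two-level factor in the week-8 between-arm comparison, and add clinical office to the data items recorded. The cost is one degree of freedom and one recorded field, with no new procedure.

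In 2.6, state whether one list or one per office is kept. If alternation is replaced by concealed random assignment, stratify that list by office; the extra cost is maintaining two strata. Do not introduce a separate alternating list for each office. Staff would then need to know only their own last patient to predict the next arm, so the gain in balance would come with easier prediction of assignments.

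Align the singular clinic in 4.2 with the two offices in CS15.2.

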Name _____ Modified Date _____

Previous IRB #:

CS1.1.1 Has this research study (or a substantially similar research study) been previously disapproved by the University of Pittsburgh IRB or, to your knowledge, by any other IRB?

* No

If **Yes**, identify the IRB, IRB number if Pitt IRB disapproved, and the primary reasons for disapproval:

View: CS02.0 - 02.1

Cover Sheet Section

CS2.0 Title of Research Study:

Pilot Study to Improve Therapeutic Outcomes for Dysphagia after Radiation Therapy

CS2.0.1 Use the textbox below to list any language or documents to be displayed in the approval letter. List only those items submitted for review with ***this submission***.

Documents to be displayed may include items such as versions of investigator brochures, consent forms, and advertisements.

If specific language is not required in the approval letter, leave the textbox blank (**do not write 'None'**).

Requested approval letter wording:

CS2.1 Research Protocol Abstract:

Patients with head and neck cancer treated with chemoradiation, often develop a treatment associated dysphagia. The common complaint is foods sticking in the pharynx. This study seeks to test the Iowa Oral Performance Instrument (IOPI) in the management of treatment induced dysphagia following chemoradiation for oral, pharyngeal, laryngeal, hypopharyngeal cancer. This pilot study seeks to compare standard exercise therapy plus

IOPI to standard exercise alone to determine if recovery is enhanced and to determine if rate of recovery is accelerated.

CS2.2 Select the category that best describes your research:

View: CS03.0 - 03.9

Cover Sheet Section

CS3.0 Name of the Principal Investigator:

[name]

Note: Adjunct faculty of the University, including lecturers and instructors, are not permitted to serve as a PI or Faculty Mentor but may serve as co-investigators. Refer to [Chapter 4](#) on the HRPO website for more information.

CS3.1 Affiliation of Principal Investigator:

UPitt faculty member

If your answer was **Other**, fill in the Principal Investigator's affiliation:

If you chose any of the **Pitt options**, please indicate the specific campus:

Main Campus - Pittsburgh

If you chose the UPitt faculty member option, provide the PI's **University Faculty Title**:
Chairperson

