1.1 **Objective: What is the overall purpose of this research study?** (Limit response to 1-2 sentences.)

To determine the effectiveness of the IOPI in the management of treatment induced dysphagia following chemoradiation for oral pharyngeal cancer.

1.2 **Specific Aims: List the goals of the proposed study (e.g., describe the relevant hypotheses**

or the specific problems or issues that will be addressed by the study).

To compare standard exercise therapy plus IOPI to standard exercise alone to determine if recovery is enhanced and to determine if rate of recovery is accelerated.

1.3 Background: Briefly describe previous findings or observations that provide the background leading to this proposal.

The IOPI device is one of the most commonly used measurement techniques available to measure tongue strength and endurance. Some research studies have indicated that it can be used to investigate influences of age, gender and medical condition on tongue strength and speech.

1.4 Significance: Why is it important that this research be conducted? What gaps in existing information or knowledge is this research intended to fill?

This is a pilot study designed to look at any enhancement the IOPI device might have, when paired with standard therapy for dysphagia following chemoradiation.

View: 2.01

Section 2 - Research and Design Methods

2.1 Does this research study involve the use or evaluation of a drug, biological, or nutritional (e.g., herbal or dietary) supplement?

* No

2.1.1 Does this research study involve an evaluation of the safety and/or effectiveness of one or more marketed nutritional (e.g., herbal or dietary) supplements for the diagnosis, prevention, mitigation or treatment of a specific disease or condition or symptoms characteristic of a specific disease or condition?

*

2.1.1.1 List each of the marketed nutritional supplements being evaluated in this research study. Specify for each supplement the corresponding IND number or attach FDA correspondence specifying that an IND is not required.

Marketed nutritional supplement

IND number

There are no items to display

Upload FDA correspondence specifying that an IND is not required, if applicable:

Name Modified Date Version

View: 2.02

Section 2 - Research Design and Methods

2.2 **Will this research use or evaluate the safety and/or effectiveness of one or more devices?**

* Yes

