2.15.3 Will biological specimens be stored **without identifiers or linkage codes?**

If you answer Yes, the samples will not be stored with any identifiers or linkage codes and it is highly unlikely to be linked back to the individual.

If you answer No, the samples will be stored with an identifier or linkage code and can be linked back to the individual.

*

View: 2.16

Section 2 - Research Design and Methods

2.16 **Will research participants be asked to provide information about their family members or acquaintances?**

* No

2.16.1 **Describe what information about the third party will be obtained from the participant:**

2.16.2 **If the information about the third party is of a private nature, can the identity of the third party be readily ascertained or associated with this information?**

*

Describe the **private information** that will be collected and recorded about the third party:

View: 2.17 - 2.18

Section 2 - Research Design and Methods

2.17 **What are the main outcome variables that will be evaluated in this study?**

1. Tongue pressure generation (strength).
2. Airway protection during swallowing (penetration-aspiration scale score of MBS data).
3. Pharyngeal residue after swallowing (pharyngeal retention scale rating of MBS data).
4. Swallowing impairment based on EAT-10, VAS, FOIS.
5. Swallow kinematic measures of MBS data on a swallow by swallow basis (videofluoroscopic image analysis with image processing software):
 - a. oral transit duration (duration of bolus transit through the oral cavity)
 - b. stage transition duration (measure of pharyngeal onset delay time)
 - c. duration of impaired oral containment (measure of bolus control in the oral cavity)
 - d. pharyngeal transit duration (duration of bolus transit from oral cavity to inferior pharynx)
 - e. pharyngeal response duration (duration of hyoid bone maximal movement during the swallow)
 - f. duration of upper esophageal sphincter opening
 - g. laryngeal closure duration (duration of airway closure)
 - h. we may analyze the magnitude of epiglottic inversion (rotation of the epiglottis during swallows which relates to laryngeal closure)

- i. we may analyze the magnitude of hyoid displacement (distance traveled by the hyoid bond during swallows)

2.18 Describe the statistical approaches that will be used to analyze the study data.

* Addressed below:

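### The rate-of-recovery aim cannot be told apart from the amount-of-recovery aim with two shared assessments, and the firm week-8 comparison leaves the collected baseline unused

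*Combined protocol and SAP*

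**What the plan says.** **Aims.** Section 1.2 gives the purpose of the comparison as "to determine if recovery is enhanced and to determine if rate of recovery is accelerated", and the abstract in CS2.1 repeats it. Section 5.12 lists a quicker recovery and a better recovery as two separate possible benefits.

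**Assessments.** Under 2.6, the VAS, EAT-10, FOIS, weight, tongue strength and modified barium swallow are obtained before therapy and again at about 8 weeks in both arms. Section 2.7 repeats the 8-week assessment. Neither section describes a visit in between. Section 2.11 gives about 8 weeks of participation for the IOPI arm and about 16 for the crossover group. The later assessment exists only for standard-arm subjects who still need therapy and agree to add IOPI.

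**Outcomes.** Section 2.17 lists tongue strength, two ratings from the swallow study, "Swallowing impairment based on EAT-10, VAS, FOIS" and kinematic measures. The durations among the kinematic measures are timings within a single swallow, not times to recovery.

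**Analysis.** Section 2.18 commits to t-tests for three sets of comparisons:

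- "between groups comparisons at time 1 (start of treatment) and at 2 (end of treatment");
- "within groups comparisons between time 1 and 2 (standard therapy vs. standard therapy + IOPI");
- "within group comparison (standard treatment crossover only) at time 1 and time 3".

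It then adds an option: "We may also perform ANOVAs and post hoc analyses to determine the main effect of treatment condition on the dependent variables". Under that same option it mentions a search for interactions of an unspecified kind ("to determine the presence of any interaction effects"), but no group-by-time term is named. FOIS, a main outcome in 2.17, is missing from the measures listed in 2.18.

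**The concern.** An aim about rate needs data on the course of recovery: at least one common assessment between start and end, or a time to some milestone. The plan has neither. Any rate it reports must be built from the same two values as the change from baseline. A favourable week-8 result could then be described both as enhanced and as accelerated recovery, with no separate evidence for the second claim.

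A smaller issue sits beside it. The firm between-arm test compares week-8 levels and does not use the baseline values that every subject provides. Allocation is by alternation (2.6), so baseline balance should not be presumed. A between-arm comparison that does use baseline can be reached only through the optional ANOVA or through one reading of the second item in 2.18.

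**Working it through.** The plan gives no figure to reproduce here. The 100 subjects are 50 + 50, and 3.12 says enrolment was set by referral base and feasibility. No alpha, effect size, SD or correlation is stated. Every numerical input below other than 50 per arm and 8 weeks is therefore an assumption.

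**1. Rate against change at a fixed interval (no assumption needed).** For each subject, rate = (week-8 value − baseline) / 8. Dividing every observation by 8 divides both the difference in means and its standard error by 8, so t and p do not move. A simulated data set of 50 + 50 gave t = −1.324, p = 0.1885 for change and the same for change/8. With two visits and complete data, a group-by-time interaction is also the same test as the difference in mean change.

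**2. Visit dates that vary.** The follow-up is only approximately at week 8. Assumed: 50 per arm, dates uniform around week 8, mean changes 6.3 and 7.96, SD of change 3.15 to 12.6, change not dependent on the exact date, 2,000 simulated trials per setting.

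| Window | Correlation of change with change per actual week | Trials in which the two t-tests differ on p < 0.05 |
|---|---|---|
| within 1 week | 0.985 to 0.997 | 1 to 4% |
| within 2 weeks | 0.942 to 0.986 | 3 to 10% |

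The two quantities are nearly, though not exactly, the same.

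**3. Faster or greater?** Assumed recovery curve: P × (1 − exp(−t/τ)), with P the plateau and τ the time constant in weeks. At t = 8:

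- control, P = 10, τ = 8: 6.32
- speed-only benefit, P = 10, τ = 5: 7.98
- plateau-only benefit, P = 12.63, τ = 8: 7.98

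Both benefits give a difference of 7.98 − 6.32 = 1.66 points, or 1.66/8 = 0.21 point per week. For control τ of 4, 6, 8, 12 and 16, with the speed-only τ at 0.625 times control, the differences are 0.95, 1.45, 1.66, 1.69 and 1.57. Plateaus of 11.1, 12.0, 12.6, 13.5 and 14.0 match them. Conversely, A × (1 − exp(−kt)) with A set so that each curve reaches 15 points at week 8 gives 4.3, 6.2 or 10.6 points at week 2 for k = 0.05, 0.2 and 0.6. The schedule would see these three curves as the same.

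**4. Could another planned item supply a rate?** Time 3 is self-selected, follows a change of therapy, has no counterpart in the IOPI arm, and is compared only within its own group. The optional C statistic, in its usual form 1 − Σ(successive difference)² / (2 × SS), is always 0 on two points: for a difference d, SS = d²/2, so C = 1 − d²/d² = 0. The exercise diary records exercise, not recovery.

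**5. What baseline adds to the between-arm test.** Assumed: true difference 0.5 SD, equal SD at both visits, two-sided alpha 0.05, 50 per arm, correlation r between baseline and week 8. Power = Φ(0.5 / (s × √(2/50)) − 1.96), with s = 1 for the week-8 level, √(2(1 − r)) for change and √(1 − r²) for the baseline-adjusted value.

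| r | Week-8 level | Change | Baseline-adjusted |
|---|---|---|---|
| 0.3 | 0.705 | 0.561 | 0.746 |
| 0.5 | 0.705 | 0.705 | 0.823 |
| 0.7 | 0.705 | 0.898 | 0.938 |

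**6. Within-group tests as a substitute.** If both arms truly change by the same amount and p is the power of each within-arm test (n = 50), the chance that exactly one is significant is 2p(1 − p). For a true change of 0.1, 0.2, 0.28, 0.4 and 0.5 SD this is 19%, 41%, 50%, 31% and 11%.

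**The case against.** The strongest reply has four parts.

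- **Enhanced recovery already has a firm test.** This stands. A reader might infer that the plan holds no committed between-arm test of recovery. The documents do not support that: 2.18 commits to t-tests between groups at time 2, and in a two-arm comparison the end-of-treatment difference is a legitimate test of effect. What remains is that it leaves baseline unused.
- **The second item of 2.18 may already compare change between arms.** A reader might take it as excluding such a comparison. It is labelled as within groups, yet its parenthesis sets one therapy against the other. It is ambiguous and should be clarified.
- **Gain over a fixed 8 weeks is an average rate, and this is a pilot.** Both are true. But that average rate is the same evidence as the gain, and 1.2 still states acceleration as something to determine. Nothing in 2.18 plans to report one result twice; the risk lies in how the aim is worded.
- **A change-score analysis would be the natural repair.** It should not be imposed. At r = 0.3 its power is 0.561, against 0.705 for the test already planned. Baseline adjustment has the highest power at each correlation shown.

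The flow chart is not available here, so a visit shown only there cannot be ruled out. However, 2.6.1 says that the chart supplements the description in 2.6, and no interim visit is described there or in 2.7.

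**Conclusion.** The point holds for the rate aim. Two shared assessments cannot distinguish faster from greater recovery. This is exact for a fixed 8-week interval and nearly so for varying dates (correlation 0.94 or more within 2 weeks, under the assumptions above). The recovery curves show that the ambiguity exists; their point values say nothing about the size of effect in this trial.

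The analysis part is an improvement, not the repair of a missing test. The week-8 comparison is firm and valid, but it forgoes baseline information worth roughly 0.04 to 0.23 in power (0.746 − 0.705 to 0.938 − 0.705) for an assumed 0.5 SD effect and correlations of 0.3 to 0.7. FOIS has no listed analysis. The plan should be changed on both counts; neither stops the trial from addressing enhanced recovery.

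**What to change.** **Aims (1.2 and CS2.1).** Delete the second half of "to determine if recovery is enhanced and to determine if rate of recovery is accelerated", or reword it as greater improvement over about 8 weeks. State that rate of recovery is not assessed separately. Section 5.12 describes possible benefit and can stay. Keeping a true rate aim would need a common interim assessment or a time-to-milestone outcome, which is a larger change.

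**Analysis (2.18).**

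- Make the firm between-arm comparison the week-8 value adjusted for its own baseline value, reported as a difference with a confidence interval.
- Apply it to every measure listed in 2.18 and add FOIS.
- Use an ordinal or rank-based version for the rating scales: penetration-aspiration, pharyngeal retention and FOIS.
- Reword the second item so that it is plainly within-group. Call all within-group comparisons descriptive, not evidence of IOPI against standard therapy.

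**Cost.** A narrower claim and a little more analysis of data already collected. No new visit, instrument or patient burden.
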